2. INTRODUCTION

2.1. Background

This Statistical Analysis Plan (SAP) is based on Amendment 1 of Protocol IMGN853-0419, dated 23 August 2021.

A brief history of protocol amendments is presented in [Table 1](#).

Table 1: History of Protocol Amendments

Version	Approval Date	Salient Changes (if any)*
Original Protocol	16APR2021	N/A
Amendment 1	23 AUG 2021	update the ocular exam requirements for assessment

*Changes expected to require accommodation in analysis plan.

This SAP will govern the analysis of study data. The plan for the primary efficacy analysis and all other analyses may be modified prior to final database lock. Any deviations from the SAP will be documented as such in the study report.

3. STUDY DESIGN

3.1. Protocol Objectives

3.1.1. Primary Objective

- To determine the efficacy of mirvetuximab soravtansine (MIRV) in patients with recurrent platinum-sensitive ovarian cancer (rPSOC) and high folate receptor- α (FR α) expression.

3.1.2. Secondary Objectives

3.1.2.1. Key Secondary Objectives:

- To determine the durability of response to MIRV in patients with rPSOC and high FR α expression.

3.1.2.2. Additional Secondary Objectives:

- To evaluate the safety and tolerability of MIRV.
- To characterize the clinical activity of MIRV in patients with rPSOC and high FR α expression.

3.1.2.3. Exploratory Objectives

- To assess the immunogenicity of MIRV.
- To evaluate potential blood-based biomarkers predictive of response to MIRV.
- To evaluate potential tumor-based biomarkers predictive of response to MIRV.
- To evaluate whether gene mutation(s) and/or homologous recombination status correlates with FR α levels.

3.1.3. Study Endpoints

3.1.3.1. Primary Endpoint

- Objective response rate (ORR), which includes confirmed best response of complete response (CR) or partial response (PR) as assessed by the Investigator.

3.1.3.2. Key Secondary Endpoint

- Duration of response (DOR), defined as the time from initial Investigator-assessed response (CR or PR) until progressive disease (PD) as assessed by the Investigator.

3.1.3.3. Additional Secondary Endpoints:

- Treatment-emergent adverse events (TEAEs) and laboratory test results, physical examination, or vital signs.
- CA-125 response determined using the GCIG criteria defined in [Appendix C](#) of the Protocol.
- Progression-free survival (PFS), defined as the time from first dose of MIRV until Investigator-assessed radiological PD or death, whichever occurs first.
- Overall survival (OS), defined as the time from first dose of MIRV until death.
- ORR, DOR, and PFS by blinded independent central review (BICR) will be summarized as sensitivity analysis.

3.1.3.4. Exploratory Endpoints

- Incidence of seroconversion of antidrug antibodies (ADA) to MIRV and association with safety and efficacy.
- Identification of blood-based biomarkers potentially predictive of responsiveness to treatment
- Identification of tumor DNA mutational status and the expression level of genes and pathways involved in cancer development, progression, and responsiveness to treatment.
- Correlation of gene mutation(s) and/or homologous recombination status with tumor FR α levels and soluble FR α levels in blood

3.2. Study Overview

This Phase 2 study is designed to evaluate the efficacy and safety of MIRV in patients with recurrent platinum-sensitive, high-grade serous epithelial ovarian cancer, primary peritoneal, or fallopian tube cancer (EOC), whose tumors express a high level of FR α , referred to throughout as rPSOC (recurrent platinum-sensitive ovarian cancer). Patients will have had at least 2 prior lines of therapy. These will include at least 2 lines of platinum-containing therapy or 1 line with a documented platinum allergy. All patients will be, in the opinion of the Investigator, appropriate for non-platinum single-agent therapy for their next line of therapy. FR α positivity will be defined by the Ventana FOLR1 (FOLR1-2.1) CDx assay (Ventana FOLR1 Assay)..

Eligible patients will receive MIRV 6mg/kg AIBW Q3W until disease progression, unacceptable toxicity, withdrawal of consent, death, or until the Sponsor terminates the study (whichever comes first).

Tumor assessments, including radiological assessments by CT/MRI scans will be performed at Screening and subsequently every 6 (± 1) weeks from C1D1 for the first 36 weeks then every 12 (± 3) weeks until disease progression, death, the initiation of subsequent anticancer therapy, or patient's withdrawal of consent, whichever occurs first. CT/MRI scans will be collected for sensitivity analysis by blinded independent central review (BICR)

Patients who discontinue MIRV for reasons other than PD will continue with tumor assessments until documentation of PD or the start of a new anticancer therapy, whichever comes first. Prior to Week 36 (from C1D1), assessments should occur every 6 weeks (± 1 week) as allowed by local requirements but must occur at an interval of no more than 12 weeks. After Week 36, assessments will occur every 12 weeks (± 3 weeks) until documentation of PD per RECIST v1.1 ([Eisenhauer 2009](#)) or the start of new anticancer therapy.

All patients who discontinue MIRV will be followed for survival every 3 months (± 1 month) until death, lost to follow-up, withdrawal of consent for survival follow-up, or End of Study (EOS) (whichever comes first). Additional survival follow-up calls may occur periodically, if needed.

3.2.1. Study Population

All patients must have a diagnosis of platinum-sensitive, recurrent high-grade serous EOC.

See [Section 3.1](#) of the protocol for a complete list of the inclusion/exclusion criteria.

3.2.2. Power and Sample Size

The primary endpoint of this study is ORR as assessed by the Investigator. The study is designed to test the null hypothesis that the ORR is $\leq 28\%$ using an optimal Simon's two-stage design ([Simon 1989](#)) without a planned pause in enrollment given preliminary efficacy and established safety of MIRV.

The optimal two-stage design to test the null hypothesis that the ORR is $\leq 28\%$ versus the alternative that the ORR is $\geq 48\%$ has an expected sample size of 37.74 and a probability of early termination of 0.762. If the ORR is $\leq 28\%$, there is a 0.024 probability of rejecting the null hypothesis (the target 1-sided alpha value was 0.025). If the ORR is $\geq 48\%$, there is a 0.9

probability of rejecting the null hypothesis. After testing the drug on 28 efficacy evaluable patients in the first stage, the study will be terminated for futility if 9 or fewer respond. If the study goes on to the second stage, a total of 69 efficacy evaluable patients will be enrolled. If the total number responding is more than 26, the null hypothesis is rejected.

Approximately 75 patients will be enrolled so that a total of 69 patients will be efficacy evaluable.

3.2.3. Treatment Randomization and Blinding

Randomization and blinding are not applicable in this single-arm, open-label study.

3.2.4. Assessment Schedule

See protocol [Table 2](#) for study schedule of assessments.

3.3. Interventions

3.3.1. Clinical Trial Material

MIRV will be administered at 6 mg/kg AIBW as an IV infusion following preparation as outlined in the Pharmacy Manual on day 1 of every 3-week cycle.

The protocol provides additional details in [Section 5.4](#).

4. GENERAL ANALYTICAL CONSIDERATIONS

4.1. Data Sources

[Section 11](#) of the protocol provides details regarding data recording and handling.

4.2. Definition of Baseline

Study Day 1 (ie, Cycle 1 Day 1) will be designated as the first day a patient receives MIRV. The baseline value is defined as the last non-missing value on or before the date of first dose of MIRV.

4.3. Missing Data

Partial dates are allowed in the clinical database for prior anti-cancer systemic therapy start and stop dates, subsequent anti-cancer therapy start date, adverse event (AE) onset and resolution dates, concomitant medication start and stop dates, and concomitant procedure, procedure dates. Dates from these forms will be reported in listings as collected. Every effort will be made to query missing dates.

For records with missing AE onset date, the following procedure will be employed for use in determining whether the AE is treatment emergent:

- AE onset dates with missing day and non-missing month will be assumed to occur on the first day of the non-missing month, except for AEs occurring in the first month of dosing, in which case the date will be the first day of dosing.
- AE onset dates with missing month will be assumed to occur on the first day of the non-missing year (i.e., January 1), except for AEs occurring in the first year of dosing, in which case the date will be the first day of dosing.

For records with a missing medication start and/or stop date, the following procedure will be employed for use in determining whether the medication is prior or concomitant:

- Medication start dates with a missing day and non-missing month will be assumed to occur on the first day of the non-missing month, except for medications occurring in the first month of dosing, in which case the date will be the first day of dosing.
- Medication start dates with missing month will be assumed to occur on the first day of the non-missing year (i.e., January 1), except for medications occurring in the first year of dosing, in which case the date will be the first day of dosing.
- Medications that are not ongoing and have a medication stop date with a missing day and non-missing month will be assumed to occur on the last day of the non-missing month.
- Medications that are not ongoing and have a medication stop date with a missing month will be assumed to occur on the last day of the non-missing year (ie, December 31).

For records with a missing procedure date, the following procedure will be employed for use in determining whether the procedure is prior or concomitant:

- Procedure dates with a missing day and non-missing month will be assumed to occur on the first day of the non-missing month, except for procedures occurring in the first month of dosing, in which case the date will be the first day of dosing.
- Procedure dates with missing month will be assumed to occur on the first day of the non-missing year (i.e., January 1), except for procedures occurring in the first year of dosing, in which case the date will be the first day of dosing.

For records with a missing prior anti-cancer systemic therapy start and/or stop date, and/or disease progression date from prior therapy, the following procedure will be employed for use in calculating the platinum-free interval (PFI):

- If the stop date of prior platinum therapy is completely missing OR only the year is available, the PFI will be set as missing.
- If both year and month of stop date of prior platinum therapy are available and only day is missing, the stop date will be imputed by the first day of the month.
- If the disease progression date from prior platinum therapy is completely missing OR only the year is available, the PFI will be set as missing.

- If both year and month of disease progression date from prior platinum therapy are available and only day is missing, the date of disease progression will be imputed by the last day of the month.

For records with a missing subsequent anti-cancer therapy start date, the following procedure will be employed for use in deriving efficacy variables such as PFS and BOR.

- The start date of subsequent anti-cancer therapy will be imputed by the earliest possible date that is not contradicting with any other available data in the database.

For records with a partial death date, the following procedure will be employed for use in deriving time to event variables (PFS, OS, DOR).

- The death date will be imputed by the earliest possible date that is not contradicting with any other available data in the database.

All other data will be reported as they are collected. No imputation methods will be used to replace missing data unless otherwise stated in this document.

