8. ASSESSMENT OF SAFETY

8.1. Recording Adverse Events and Serious Adverse Events

AEs, including those attributed to study procedures, will be documented in the clinical trial database and monitored continuously throughout the study from the time of informed consent until 30 days after the patient's last study treatment.

Document ID: CLIN-00067	Title: IMGN853-0419 Clinical Study Protocol	Version: 2.0
Legacy ID: 26587		Approved Date: 12/22/202

Only AEs/SAEs which are considered related to a study procedure (ie, blood draw or fresh tumor biopsy) will be captured during the pre-screening period, ie, from the time of signing of the pre-screening informed consent (if one is utilized) until the time of signing of the main study informed consent, or until the patient is determined to be a screen failure. All AEs and SAEs, regardless of causality, will be captured after the main study ICF has been signed.

SAEs will continue to be followed by ImmunoGen Pharmacovigilance until resolution, stabilization, or return to baseline. Beyond this defined reporting period, any unsolicited SAE assessed as related to the study drug by the Investigator and reported to ImmunoGen will be collected and processed. Additional information obtained after database lock, will reside solely in the safety database.

The Investigator should follow and provide updates for all AEs until clinical recovery is complete, laboratory values return to normal, the patient stabilizes, or death occurs, to ensure the safety of the patients. This may mean that observations continue beyond the last planned visit per protocol and that additional investigations may be requested by the Sponsor.

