7.2. AEs

AEs will be documented on the AE CRF and monitored continuously throughout the study from the time of informed consent until 30 days after the patient's last MIRV or until the event has resolved, stabilized, or returned to baseline. AEs attributed to study procedures, including those events that occur prior to the first dose, should also be documented on the AE CRF.

AE data are available to ImmunoGen from 2 sources, the clinical database and the serious adverse event (SAE) forms. While reconciliation will be performed, the production of data summaries and listings will be based on the data collected on the clinical database.

Pre-treatment AEs are defined as AEs with an onset date prior to the first dose of MIRV. TEAEs are defined as AEs with an onset date on or after the first dose of MIRV, and within 30 days of the last dose of MIRV or prior to the start of a new anti-cancer treatment, whichever occurs first. Medical history conditions that exist before the initiation of MIRV but worsen in severity during the study will also be recorded on the AE CRF as an AE and will be included as treatment-emergent in the summary tables and listings.

The adverse events will be coded using MedDRA (Version 24.0 or later), associating lower-level terms with PT and SOC by the primary hierarchy. The tables will display the counts and percentages of patients who reported at least 1 TEAE in each SOC represented in the AE data. Within each SOC, the tables will display the counts and percentages of patients reporting at least 1 TEAE as designated by the PT.

AEs are graded using CTCAE Version 5.0. AE summaries may include summaries for all AEs and by the maximum CTCAE grade for the item being summarized (ie, SOC or PT). In these cases, the outputs will include a row for All Grades as well as rows for the 5 potential CTCAE grades, Grade 1 (Mild), Grade 2 (Moderate), Grade 3 (Severe), Grade 4 (Life threatening or disabling), or Grade 5 (Death). AEs missing a severity grade will not be included in the Grade 1-5 rows of the tables. An AE reported by a patient more than once will be represented in the most severe category TEAEs will be categorized as MIRV-related if "Possibly Related", "Probably Related", or "Definitely Related" is selected by Investigator. AEs missing relationship to MIRV will be included in the Related TEAE tables.

The following AE summary tables will be produced.

- An overall summary of TEAEs
- All TEAEs by SOC and PT
- TEAEs by PT

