- Serious TEAEs by SOC and PT
- Grade 3 or higher TEAEs by SOC and PT
- TEAEs leading to drug withdrawal by SOC and PT. This subset includes TEAEs with an action taken of drug permanently discontinued.
- Related TEAEs leading to drug withdrawal by SOC and PT. This subset includes TEAEs related to MIRV with an action taken of drug permanently discontinued.
- TEAEs related to MIRV by SOC and PT.
- Serious, related TEAEs by SOC and PT.
- TEAEs leading to dose modifications (dose reduction, dose held, or dose delay) by SOC and PT.
- Related TEAEs leading to dose modification (dose reduction, dose held, or dose delay) by SOC and PT.
- Deaths on study treatment or within 30 days of the last dose. This table includes all deaths during study treatment or within 30 days of the last dose, regardless of cause of death.
- TEAEs leading to death. This table includes all TEAEs with CTCAE Grade 5.
- Related TEAEs leading to death. This table includes all TEAEs related to MIRV with CTCAE Grade 5.

The following listings will be produced:

- All AEs, sorted chronologically by patient. This listing includes SOC, PT, onset and end dates, and other relevant information.
- Serious TEAEs, sorted chronologically within patient.
- TEAEs leading to drug withdrawal. This subset includes TEAEs with an action taken of drug permanently discontinued.
- TEAEs leading to dose reduction.
- TEAEs resulting in death. This listing includes TEAEs with a CTCAE grade of Grade 5 (death).
- All deaths, with an indication of whether the death occurred on study or within 30 days of the last dose.

The following groupings of TEAEs will be generated as part of the focused analysis of safety:

- Ocular TEAEs.

- A list of PTs for ocular AEs will be provided and finalized by the Sponsor before the final database lock.
- Peripheral neuropathy TEAEs.
 - A list of PTs for peripheral neuropathy AEs will be provided and finalized by the Sponsor before the final database lock.
- Pneumonitis

Additionally, tables will be produced which contains the following.

- TEAEs by PT and maximum CTCAE grade
- Time to first onset of TEAEs.
- Action taken of TEAEs.
- Resolution of TEAEs

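### SAP 4.3 moves a partial AE onset to the first-dose date without checking the AE end date, so a screening AE already resolved before dosing is flagged as treatment-emergent

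*SAP*

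**What the plan says.** SAP 4.3 allows AE onset and resolution dates to be partial. For an incomplete onset, "the following procedure will be employed for use in determining whether the AE is treatment emergent":

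- Day missing, month known: the first of that month, "except for AEs occurring in the first month of dosing, in which case the date will be the first day of dosing".
- Month missing, year known: 1 January of that year, "except for AEs occurring in the first year of dosing, in which case the date will be the first day of dosing".

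SAP 7.2 then separates the two classes by onset alone. "Pre-treatment AEs are defined as AEs with an onset date prior to the first dose of MIRV", and "TEAEs are defined as AEs with an onset date on or after the first dose of MIRV", up to 30 days after the last dose or the start of new anti-cancer treatment. It makes no exception for an event that ended before dosing.

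Pre-dose AEs are in the database. Protocol 8.1 states that "All AEs and SAEs, regardless of causality, will be captured after the main study ICF has been signed", and procedure-related events are also captured during pre-screening. End dates are in the database too. On the listing of all AEs, SAP 7.2 says: "This listing includes SOC, PT, onset and end dates, and other relevant information".

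Elsewhere in SAP 4.3, imputed dates are checked against other data. For deaths: "The death date will be imputed by the earliest possible date that is not contradicting with any other available data in the database". The start of subsequent therapy has the same condition. SAP 4.3 also says that missing dates will be queried and that listings show dates as collected.

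**The concern.** Assigning an onset of unknown timing to the first-dose date is a sensible conservative default. It stops being sensible when the AE's own end date settles the question. If the event is recorded as resolved before first dose, it cannot have begun on treatment, yet the rule as written says that it did.

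TEAEs are a named secondary endpoint (SAP 3.1.3.3), and the trial has a single arm, so there is no comparator in which similar misclassification would occur. A false TEAE enters the TEAE tables and the time-to-first-onset output of SAP 7.2. In the derived data its onset falls after its end.

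**Working it through.** The documents give no figure on this point, so there is nothing to reproduce. The check applies the SAP 4.3 and 7.2 rules as written to constructed records. It reads the first month or year of dosing as the calendar month or year of first dose.

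**Step 1: the rule.** First dose is 20 March 2022 in every row.

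| Recorded onset | Recorded end | Imputed onset | Class as written | Class with an end-date check |
|---|---|---|---|---|
| March 2022, day missing | 10 March 2022 | 20 March 2022 | TEAE, onset 10 days after end | Pre-treatment |
| 2022, month missing | 10 March 2022 | 20 March 2022 | TEAE, onset 10 days after end | Pre-treatment |
| February 2022, day missing | 10 March 2022 | 1 February 2022 | Pre-treatment | Pre-treatment |
| March 2022, day missing | 25 March 2022 | 20 March 2022 | TEAE | TEAE |

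Only the first two rows are wrong. The fault needs three things together: a partial onset, a known month (or year, if the month is missing) equal to that of first dose, and an end date before first dose.

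**Step 2: how often a screening day falls in the affected month or year.** Protocol Table 2 allows screening up to 28 days before Cycle 1 Day 1, with some assessments limited to 14 days. Assume first-dose dates spread evenly over 2022. For a first dose on day d of a month, the number of the preceding 28 days in the same month is min(28, d − 1), which ranges from 0 to 28.

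- Sum over a 31-day month: 462. Over a 30-day month: 434. Over February: 378.
- Year total: 7 × 462 + 4 × 434 + 378 = 5,348. Share: 5,348 / (365 × 28) = 0.523.
- The same calculation for 14 days: (7 × 329 + 4 × 315 + 287) / (365 × 14) = 3,850 / 5,110 = 0.753.
- Same calendar year, 28 days: only first doses on 1 to 28 January lose days, 28 + 27 + … + 1 = 406 in all. Share: (10,220 − 406) / 10,220 = 0.960.

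**Step 3: an illustrative count.** The documents give no rate of pre-dose AEs, of their resolution before dosing, or of missing onset days. Assume 75 patients, one pre-dose AE each, spread evenly over a full 28-day window, with 2% to 5% lacking the onset day after querying.

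Count = 75 × (share resolved before dosing) × (share with day missing) × 0.52

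- All resolved: 75 × 1 × 0.02 × 0.52 = 0.8, to 75 × 1 × 0.05 × 0.52 = 2.0.
- Half resolved: 0.4 to 1.0.
- All missing days recovered by query: 0.

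This covers missing days only. A missing month would be caught in about 96% of cases, but the documents give no basis for a rate.

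**Step 4: effect on a table row.** Tables count patients with at least one event, so one false TEAE adds at most 1 / 75 = 1.3%. It adds nothing if the patient already has a genuine TEAE of that term.

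**The case against.** The strongest reply is that this hardly ever happens. Missing dates are queried, and a record with a full end date but only a month or year of onset, within a short screening period, is an obvious query. That stands as a reason to expect few records. It does not repair the rule, which exists for dates that stay partial.

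A second reply is that the wording is open: an AE that ended before dosing arguably did not occur in a month of dosing. The phrase is indeed undefined. But the bullets do not tell the programmer to look at the end date, so the favourable reading needs to be written down.

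A third is that the condition attached to death and subsequent-therapy dates is no precedent, because an earliest-possible-date rule needs a bound and the AE rule names a specific date. That is fair. The comparison shows only that checking against other data is already part of this section.

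A reader might also infer that the listings will show impossible dates, or that the serious, Grade 3 or higher and related tables will be visibly inflated. The documents do not support this. Listings keep the collected dates. Serious events have their own form, due within 24 hours of the Investigator learning of the event (Protocol 8.2.1), and the two sources are reconciled (SAP 7.2), so an unresolved onset date for a resolved screening SAE is improbable. A pre-dose event with no assessed relationship to drug reaches the related tables only if the relationship is left missing.

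**Conclusion.** The rule is wrong as written, but minor. For a partial onset in the month of first dose (or the year, if the month is missing), SAP 4.3 and 7.2 together classify a screening AE as treatment-emergent even when its recorded end date precedes first dose. The consequence is limited to the derived TEAE flag and what is built on it.

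The number of affected records is unknown and probably small. The figure of 0 to about 2 is an upper-end illustration resting on the assumptions in the working, not an estimate from the documents. The direction is to overstate toxicity, so no safety signal is hidden. Safety carries no hypothesis test and the ORR analysis is unaffected.

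**What to change.** Add to both AE onset bullets in SAP 4.3:

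> unless the AE end date (complete or partial) shows that the event resolved before the first dose, in which case the AE is classified as pre-treatment. Any imputed onset must not be later than the AE end date or conflict with other recorded data (for example, fall before informed consent for an AE collected after consent).

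Keep the first-dose default when the end date is missing, inconclusive, or on or after first dose.

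Setting the class directly is better than reverting to the first of the month or 1 January. With consent on 25 August 2022, onset recorded only as 2022 and end on 8 September 2022, reverting would give 1 January 2022: the right class, but an onset almost eight months before consent.

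The cost is a sentence or two in the SAP and one condition in the AE dataset program. SAP 2.1 permits changes before final database lock. After that, the same correction can be documented in the study report as a deviation from the SAP.
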